The testing session is expected to take 45 to 60 minutes, depending upon the attention span and cooperation of the child; this includes regular breaks and relaxation points. It will not be possible to blind the researcher as to which group test participants have been allocated, as those patients with strabismic amblyopia will likely be easily identified due to the presence of their strabismus.

Background information will be recorded on data collection sheets (Appendix 1), and results of the vision tests are recorded as data files on the experimental/display computer. Participants need only complete one testing session, but may complete to 3 sessions over the 24 month period. Additional sessions would allow for analysis change over time. Participants

are free to decide on the length of their participation and can leave the study at any time.

Background information

Prior to testing, the following relevant clinical information will be taken from the patient's digital medical records, or measured and recorded by the PI who is a registered Orthoptist;

- 1. Age
- 2. Gender
- 3. Diagnosis and Amblyopia subtype
- 4. Identification of fellow and amblyopic eye
- Most recent SLT visual acuity result for each eye, for healthy volunteers this will be assessed by the PI.
- 6. Current refractive correction
- Stereoacuity measurement. For healthy volunteers this will be assessed by the PI to ensure inclusion criteria are met.

This information will be used to identify which group the participant will be recruited to (anisometropic, strabismic or control) and also to aid randomisation of initial testing eye within each group. The participant will also be allocated a participant number and all results will be recorded using this participant number to preserve anonymity.

Randomisation

Each group will undergo covariate adaptive randomisation using minimisation to select which eye will be examined first (Hu et al., 2014). Test participants will have either their Amblyopic eye (AE) or Fellow eye (FE) assessed first for all 3 experiments, and control participants will have either their Right eye (RE) or Left eye (LE) assessed first. This will ensure equal distribution of known confounding variables (e.g. amblyopia density, occlusion regime, gender) for testing order bias between eyes. This minimisation process will allow for better statistical analysis and extrapolation of results. The order of experiments will be counterbalanced to prevent testing order bias.

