It will not be possible to guarantee equal distribution within groups across age, as it is expected that most recruited participants will be around 5 years of age because the National Vision Screening programme occurs during the first year of school.

Materials

The presentation and control of visual stimuli will use custom-written Matlab programmes (MathWorks[™], Natick, USA), using the 'Psychophysics Toolbox Version 3 (PTB-3)' on a 15"MacBook Pro with Retina Display, operating an Intel HD 630 Graphics card. The monitor will be calibrated and gamma corrected using an OptiCal photometer (Cambridge Research Systems). This will secure a linear progression of luminances, ensuring the input selected matches the luminance output produced, allowing for correct interpretation of the results. The screen resolution will be set to the highest possible spatial resolution (1920x1200 pixels)

16

and the frame rate will be set to the highest frame rate compatible with the aforementioned spatial resolution.

Optotypes for the 'Enhanced Cambridge Crowding Test', 'Contrast-modulated Cambridge Crowding Test' and the 'Crowding Distance Test' will each be printed onto respective matching cards, allowing for participants to point to what they see, if they are unable or unwilling to name the displayed visual stimuli.

Methodology

All participants will have the tests explained to them in the form of an astronaut story and they will complete tasks (the 3 modified vision tests) in order to help the astronaut complete his/her missions successfully. This will ensure that the examination is fun and engaging, with the aim of improving compliance and concentration. The eye not being tested will be occluded with an eye patch, or a patch that clings to a spectacle lens. All assessments will be completed at 3m, as this will allow the researcher to sit near the child so they can encourage compliance. Amblyopic eyes may be moved closer to the screen to accommodate for their poorer vision, and their threshold scores recalculated accordingly.

Staircase procedures will be used to measure vision (Lalor, 2018; Pelli, Waugh, Martelli *et al*, 2016; Waugh *et al.*, 2018). The staircase is a quick, efficient and popular method of determining an accurate visual acuity threshold; it is therefore an appropriate method of evaluating visual acuity thresholds with young children in clinical settings (Cornsweet, 1962; Corwin, Kintz and Beaty, 1979; Witton, Talcott and Henning, 2017).

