Contrast-modulated optotypes for the 'Contrast-modulated Cambridge Crowding Test' are created using dynamic noise (Smith and Ledgeway, 1997) to ensure that static luminance clumps are not useful for identifying them. Optotypes can then only be extracted by the visual system using differences in contrast, not luminance (see Figure 5). For each stimulus frame, different binary (black or white) checks of noise are drawn onto the screen and the noise is multiplied by a square-wave optotype profile. The screen cycles through several noise pages every 4 temporal frames (tied to the temporal resolution limit of the screen), so that the noise appears to twinkle in time. The size of the black and white noise checks on the stimulus screen is scaled to the overall optotype size, such that each letter consists of 15 noise checks, which has been found to be most effective for measurement of vision (Pelli and Farell, 1999) and ensures that the noise is resolvable at all optotype sizes.

Experiment 1 – Enhanced Cambridge Crowding Test

The participant will be shown the Cambridge Crowding Test letter matching card prior to the start of the experiment, and asked to name the letters, with whatever names they wish to

19

use. If they cannot do this with ease, they will be allowed to match what they see, by pointing

to an optotype on the matching card (see Figure 4).

[figure not shown]

Figure 4: "Enhanced Cambridge Crowding test" matching card

A laterally-reversible target letter (e.g., H, O, T or V) will be displayed and surrounded by four other letters (U, A, L, C) as per the Cambridge Crowding Test (Atkinson et al., 1988). The surrounding letters will be placed 1 stroke-width away from the target letter (see Figure 1). Isolated letters will also be presented. The child will identify the central letter only. Once threshold is reached the experiment will stop. After a short break, the second eye is tested in the same manner. It is expected that this should take approximately 5 minutes based on pilot experiments. This is the end of experiment 1. [name] – Amblyopia research protocol 5.0 IRAS Number: 238449

Experiment 2 – Contrast-modulated Cambridge Crowding Test

The participant will again be allowed to match (see Figure 5) or name the visually displayed optotypes.

[figure not shown]

Figure 5: "Contrast Modulated Cambridge Crowding Test" matching card

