A contrast modulated letter will be displayed on the computer screen in an arrangement as per Experiment 1, with the surrounding letters placed 1 stroke-width away from the target letter. The participant will identify the central letter, the size of which will vary according to the staircase procedure until size threshold is reached; then the experiment will stop. Examination of both eyes will take approximately 5 minutes, including a comfort break, based on pilot experiments.

Experiment 3 – "Crowding Distance Test"

The participant will be shown the "Crowding Distance Test" matching card prior to the start of the experiment, and ask to name the numbers. They will be able to indicate what they see by either calling out the number or pointing to it on the matching card (see Figure 6).

Figure 6: "Crowding Distance Test" matching card

A trigram arrangement (a trio of numbers) with 1 stroke width separation, will be presented according to an adaptive staircase procedure. The child will identify the central number and visual threshold will be established using a staircase procedure. The second eye will be examined in the same manner taking approximately 5 minutes, based on pilot experiments.

Following a short break, repeated numbers (two repeating numbers that fill the screen) separated by 1 stroke width separation, will be presented. The repeated arrangement is helpful when eye movements are unstable, as it allows the eye to find the target optotype regardless of where on the screen it lands. This procedure will be repeated with the other

eye. The anticipated time to complete the measure in both eyes is around 5 minutes. This is the end of Experiment 3, and the end of the testing session.

The order of tests or experiments will not always be the same, but will be counterbalanced across participants within any experimental group to ensure that thresholds are not biased due to practice, attention, or fatigue effects.

Throughout the study, participants will be offered stickers and stamps on a 'passport' to maintain interest and concentration, as well as making the study fun and engaging. The tests follow a story line about a teddy astronaut visiting outer space, and alien toys helping the participants to interpret the signs (optotypes) along the way. Soft toy teddies and aliens will decorate the room and be available to help the child if need be. This has been found to be helpful particularly with young children (Waugh *et al*, 2018).

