Following completion of the vision tests, participants will be asked if they wish to be involved again with the study. If they do, then they will be tested again following their next Orthoptic review with the ACPOS clinic, or at a time that suits the family best. If they do not, this is the end of their participation.

Consideration of measurement tools, validity and reliability

The results will be generalizable to the entire UK screening population of 3 to 11-year-olds, due to the use of a control group, ensuring external validity.

Participant bias will be controlled and intra-observer reliability maximised using the rigorous set of forced-choice psychophysical testing procedures described above and a single specialized researcher. The researcher is a qualified clinical Orthoptist with many year's experience working with children in vision screening clinics, ensuring that the results will be obtained as accurately and consistently as possible. Test/re-test reliability is ensured by the use of randomization of the order in which the eyes are examined, and counterbalancing the order of the experiments.

Statistical consideration and Data management and analysis

Anonymised data from the 3 experiments will be stored digitally on the experimental computer, which is password protected and only accessible to members of the research team. Data will be compiled in an Excel spreadsheet, ready for analysis.

The data will be analysed using SPSS or Statistica with Repeated Measures Analysis of Variance models. Visual acuities, crowding and critical spacing estimates will be compared between normal and amblyopic groups. Confirmation of normality and sphericity will be assessed with a Shapiro-Wilk test and Mauchley's Test of Sphericity and where necessary, error rates will be adjusted with a Huynd-Feldt Correction in order to ensure that type 1 errors (incorrect rejection of the null hypothesis) are less likely. The rate of improvement of visual acuity, crowding and critical spacing over the treatment period will also be compared (in those participants who opt to complete more than one assessment session) between the three modified tests, and the SLT.

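### The first-tested eye is assigned by minimisation, but the planned ANOVA names no eye-order term, so any second-eye effect would stay in the error of the inter-ocular difference

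*Combined protocol and SAP*

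**What the plan says.** The Randomisation section states: "Each group will undergo covariate adaptive randomisation using minimisation to select which eye will be examined first". The order is then fixed for the child: "Test participants will have either their Amblyopic eye (AE) or Fellow eye (FE) assessed first for all 3 experiments"; controls have right or left eye first on the same basis. The section names amblyopia density, occlusion regime and gender as examples of the variables to be balanced, and adds: "This minimisation process will allow for better statistical analysis and extrapolation of results". The three experiments are also rotated: "The order of experiments will be counterbalanced to prevent testing order bias". The text closing Experiment 3 repeats that the order is "counterbalanced across participants within any experimental group", and gives practice, attention and fatigue as the reasons.

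Within an experiment both eyes are tested in succession. For Experiment 1: "After a short break, the second eye is tested in the same manner".

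On analysis, the section on statistical consideration, data management and analysis states: "The data will be analysed using SPSS or Statistica with Repeated Measures Analysis of Variance models". It and the Sample Size section add normality and sphericity checks, a Huynh-Feldt correction, Tukey or Dunnett comparisons and Bland-Altman agreement. Neither names eye order, test position or a minimisation variable as a model term. Neither lists the within-subject or between-subject factors at all.

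**The concern.** The plan treats order effects as real enough to design against, and promises an analytic benefit from doing so, but never says how the analysis will use the design. Balance removes the average bias from order. It does not remove the spread: a second-eye shift d moves a child's signed inter-ocular difference by +d or −d according to which eye went first. Without an order term, that spread is counted as random error although the design has already taken it out of the estimate. Standard errors are then too wide and power is lost.

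The inter-ocular difference is the quantity in the research question. Children aged 3 to 11 in a session of 45 to 60 minutes could plausibly show practice or fatigue.

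**Working it through.** **The plan's own figures.** Sample Size sets an effect of 0.100 logMAR, an SD of 0.100, two-sided alpha 0.05 and power 0.80.
- Two means: n = 2 × (1.960 + 0.842)² / 1² = 15.7, so 16 per group, as stated. (The exact noncentral t gives power 0.781 at 16 and needs 17.)
- Three-group one-way ANOVA, Cohen's f = 0.4, 21 per group: noncentral F power 0.798, matching the stated design, with nothing in reserve.

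**Model.** Inter-ocular difference = group mean + s·d + error, with s = +1 or −1 for eye order (balanced) and error SD σ. Residual variance is σ² with an order term and σ² + d² without it. The documents give no value for d, so d = 0.03, 0.05 and 0.08 logMAR are assumptions.

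**Choice of σ.** The plan's 0.100 is set for the acuity measure. New-test-minus-SLT inter-ocular difference combines four measurements. If they were independent with SD 0.10 each, σ = √4 × 0.10 = 0.20. I therefore use 0.10 to 0.20 as the range.

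**Variance inflation, d²/σ²:**

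| d (logMAR) | σ = 0.10 | σ = 0.20 |
|---|---|---|
| 0.03 | 0.0009/0.01 = 9% | 0.0009/0.04 = 2% |
| 0.05 | 0.0025/0.01 = 25% | 0.0025/0.04 = 6% |
| 0.08 | 0.0064/0.01 = 64% | 0.0064/0.04 = 16% |

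**Hypothesis 1, new test against SLT.** Simulation with 42 amblyopes, order split 21/21, at the plan's 0.10 logMAR effect:
- σ = 0.10: power above 0.999 with or without the term, at every d.
- σ = 0.20: about 0.885 with the term; 0.883, 0.874 and 0.851 without it. The largest loss is 0.885 − 0.851 = 0.034.

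The direction of the error is conservative: at σ = 0.10 and d = 0.05, the nominal 5% test without the term runs at about 2.7%.

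**A comparison of two groups of 21** (difference 0.10, σ = 0.10, d = 0.05): simulated power 0.83 without the term and 0.88 with it; mean standard error 0.0344 against 0.0306.

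**Three-group ANOVA, 21 per group.** Without the term the effective f is 0.4/√(1 + r²), where r = d/σ. For r = 0.3, 0.5 and 0.8 this is 0.383, 0.358 and 0.312. Simulated power is about 0.76, 0.70 and 0.54, against about 0.80 with the term. (The noncentral F with the reduced f agrees at the first two values and gives 0.57 at the third. It treats order as random noise in the estimate as well, which a balanced design avoids.)

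**Cost if d = 0.** Power in the ANOVA is 0.797 with the term against 0.798 without.

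**Where the shift cancels.** The same eye goes first in all three new tests, so a common d drops out of contrasts among them. It does not drop out between groups. Nor can it be relied on to drop out against SLT, which for clinic patients is the most recent recorded result, with no eye order stated. A test-position shift common to both eyes also cancels, because both eyes are tested inside each experiment. With a position shift of 0.05 logMAR per place, the simulated standard error of the inter-ocular difference stayed at 0.0306.

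**The case against.** The best case against the point has four parts.

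- **The order effect is assumed.** This stands. At d = 0.03 and σ = 0.20 the inflation is 2%, and the loss for Hypothesis 1 is negligible.
- **Silence is not exclusion.** This stands in part. The plan names a model family and lists no factors, so eye order is no more ruled out than eye or test. But leaving the terms open means they can be chosen after the data are seen, and the plan's promise of better analysis is not made good.
- **Estimates stay unbiased and tests err on the safe side.** True, apart from the trivial imbalance of 11/10 in a group of 21. This limits the point to precision and power. A reader might infer that the trial's results would be biased; the design does not support that.
- **Test order is not a source of noise in the inter-ocular difference.** Correct. A reader might infer from the missing test-position term that it is, but a shift common to both eyes cancels. Position matters for comparisons of threshold or crowding level between tests. It would matter for the inter-ocular difference only if the first-to-second-eye effect changed with position, which nothing in the documents indicates.

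A reader might also take "It will not be possible to guarantee equal distribution within groups across age" to mean that age is left out of the minimisation. It does not say that. It concerns the spread of ages within groups, and Age is on the background list that the protocol says will help to randomise the first eye.

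**Conclusion.** The point holds for eye order only, and as a matter of precision. An assigned, balanced design factor has no stated place in the analysis. If a second-eye effect exists, between-group and new-test-versus-SLT comparisons of inter-ocular difference will be conservative; contrasts among the three new tests are largely unaffected.

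For Hypothesis 1 at the plan's effect size, the cost is nil to about 3 points of power. It matters more for the three-group comparison behind Hypothesis 2, which starts at about 0.80 and would fall to about 0.76, 0.70 or 0.54 at d of 0.3, 0.5 or 0.8 SD. These sizes rest on assumed values of d, on an assumed SD of 0.10 to 0.20 for the inter-ocular quantity, and on signed differences with near-even eye order. The documents do not show that power will be lost; they show that nothing in the written analysis prevents it, although prevention is almost free.

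**What to change.** Add the following to the statistical consideration and data analysis section:

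- Every model of inter-ocular difference includes eye tested first as a between-subject factor: amblyopic or fellow eye in amblyopes, right or left eye in controls, coded within group. If eye is instead kept as a within-subject factor, the order-by-eye interaction is included.
- Models of threshold or crowding level include the test's position in the session (first, second or third).
- The estimated order effects are reported.

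Gender may be added as a minimisation factor common to all groups. Do not adjust for amblyopia density where it is derived from the SLT inter-ocular difference, because part of the outcome would then stand on both sides of the model.

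Confirm that eye order and test position are captured for each child; the background information list does not name them, and the data sheet itself is not available here.

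The cost is a few sentences of text and one or a few degrees of freedom, about 0.001 of power if there is no order effect. It needs no extra children or visits. No change to age balancing or to repeat sessions is needed for this point.

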These figures produce an estimated total sample size of n=32 for testing Hypothesis 1 (16 amblyopes and 16 controls), and n=63 for testing Hypothesis 2 (21 anisometropic amblyopes, 21 strabismic amblyopes and 21 controls).

In order to fulfil both these criteria for hypotheses 1 and 2, and achieve statistical significance, we will recruit n=21 in each group (anisometropic amblyopes, strabismic amblyopes and control participants), with a total recruitment number n=63.

Recruitment and identification of participants:

The study will be publicised in a number of ways.

- 1. A poster will be displayed in the waiting room of the ACPOS clinic in order to raise awareness of the study to those who attend the clinic (Appendix 1).
- 2. Clinicians / the direct care team at ACPOS, will identify eligible participants during their clinical appointments, and offer them a study information leaflet. ACPOS will be the Patient Identification Point (PIC). An application will be made for the Principal Investigator to have a research passport (letter of access/ honorary research contract) in order to help identify potentially suitable participants attending the ACPOS clinic. The Principal Investigator is suitable for this task as she worked as the clinician in this clinic prior to starting this study.

Interested persons will be given the parent / guardian and paediatric information sheets (Appendix 1) and their medical history checked to ensure they meet all the inclusion criteria and none of the exclusion criteria, prior to recruitment. For ACPOS individuals who do not wish to take part, the clinician will add an addendum to the participant's clinical notes to ensure that the participant is not approached again as a potential participant.

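### Repeated-measures ANOVA drops a child from any model in which one of that child's thresholds is missing, and the plan has neither a missing-data rule nor spare recruitment for Hypothesis 2

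*Combined protocol and SAP*

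**What the plan says.** **Method.** Under Statistical consideration and Data management and analysis: "The data will be analysed using SPSS or Statistica with Repeated Measures Analysis of Variance models". The section adds a Shapiro-Wilk test, Mauchly's test and a Huynh-Feldt correction. Neither it nor Sample Size, which names the same method again, says what happens to a child with an unfinished threshold. There is no imputation, analysis-set definition or replacement of withdrawn children.

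**Session.** Under Study procedure: "The testing session is expected to take 45 to 60 minutes, depending upon the attention span and cooperation of the child". Participants "are free to decide on the length of their participation and can leave the study at any time".

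**Thresholds per child.**
- Experiment 1 measures crowded letters in each eye, and "Isolated letters will also be presented".
- Experiment 2 measures contrast-modulated letters: "Examination of both eyes will take approximately 5 minutes, including a comfort break, based on pilot experiments".
- Experiment 3 measures number trigrams ("The second eye will be examined in the same manner taking approximately 5 minutes, based on pilot experiments") and then repeated numbers ("This procedure will be repeated with the other" eye).
- The Sonksen logMAR Test (SLT) result for each eye comes from the clinical record or from the principal investigator.

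**Recruitment.** Sample Size requires 16 per group for Hypothesis 1 and 21 per group for Hypothesis 2. It recruits the larger number, "with a total recruitment number n=63".

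**The concern.** Classical repeated-measures ANOVA needs every within-child cell of the fitted model. A child who tires and leaves one staircase undone is removed from that model, and the thresholds the child did give to it are lost as well. The protocol expects tiredness: under Methodology it allows fewer averaged reversals according to age, concentration and attention. That shortens a staircase but does not deal with one that is never finished. The optional repeat sessions are meant for studying change over time, not for filling gaps.

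Two things are at stake. The first is power for Hypothesis 2, where the number recruited equals the number required. The second is selection. If unfinished staircases are commoner in younger children or in those with denser amblyopia, the complete cases over-represent children who find the tests easy. This would weaken the protocol's claim that results generalise to UK 3 to 11-year-olds, and recruiting more children would not cure it.

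**Working it through.** **1. Reproduce the plan's figure.** Inputs from Sample Size: one-way ANOVA, three groups, Cohen's f = 0.4, two-sided α = 0.05, N = 63. The noncentrality is N·f² = 63 × 0.16 = 10.08, with 2 and 60 degrees of freedom. Power is 0.798, which reproduces the stated 80%. The first equal-group size strictly above 0.80 is 22 per group (N = 66, 0.818), so 63 has no slack.

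**2. Count the staircases.** Experiment 1: crowded and isolated letters × 2 eyes = 4. Experiment 2: 2. Experiment 3: trigrams and repeated numbers × 2 eyes = 4. The total is 10, or 8 if isolated letters have no staircase of their own.

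**3. How many enter one model?** The documents do not say. One new test against the SLT across eyes uses 2 staircases (plus the SLT). Three new tests and the SLT, with one condition from each experiment, use 6. Everything together uses 10.

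**4. Complete children.** With m staircases in a model, each missing independently with probability p, the complete share is (1 − p)^m. The documents give no p, so 1%, 3% and 5% are assumed. The SLT is taken as complete because ability to do it is an inclusion criterion. Power is the calculation of step 1 with N = 63 × (1 − p)^m.

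| Staircases in model | p = 1% | p = 3% | p = 5% |
|---|---|---|---|
| 2 | 98%, 62 children, 0.79 | 94%, 59, 0.77 | 90%, 57, 0.75 |
| 6 | 94%, 59, 0.77 | 83%, 52, 0.71 | 74%, 46, 0.65 |
| 10 | 90%, 57, 0.75 | 74%, 46, 0.65 | 60%, 38, 0.55 |

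Example: 0.95^10 = 0.599; 63 × 0.599 = 37.7; power 0.55.

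The plan's power formula takes one summary value per child. It serves here as the plan's own yardstick for the number of complete children, not as the exact power of a repeated-measures test.

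**5. Hypothesis 1.** Inputs: difference 0.100 logMAR, SD 0.100, so d = 1. The normal approximation gives 16 per group, as stated. The trial will have 42 amblyopes and 21 controls, for which the two-sample t-test has power 0.957. In the worst case of step 4 (38 complete children, about 25 against 13) it is still 0.81.

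**The case against.** The strongest case on the other side has five parts.

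- **One ten-cell model is not stated.** The analysis section speaks of models in the plural and lists acuity, crowding and critical spacing as outcomes. Deletion works model by model, so a child with nine good thresholds need not be lost from everything. This stands. The plan to compare the new tests with each other and with the SLT points to joint models, but does not establish a ten-cell one.
- **Ten staircases is an inference.** Isolated letters are mentioned in one sentence, without a separate staircase. This also stands.
- **Only the secondary question loses meaningful power.** A reader might infer that the trial as a whole becomes underpowered. The documents do not support that: at the planned d = 1, Hypothesis 1 has ample reserve.
- **There are safeguards.** Amblyopic eyes may be tested closer to the screen, reversals can be cut from 4 to 2, and there are matching cards, breaks and a game format. The stated testing blocks add up to roughly 20 minutes (four of about 5); the 45 to 60 minutes includes breaks. This makes the higher missingness rates less certain, but none of it says how to analyse a threshold that is still missing.
- **Who would be lost is conjecture.** A reader might infer that the youngest or densest amblyopes will be dropped and the result biased. The link to age is plausible, since the protocol ties shortened testing to age and attention; the link to amblyopia depth is inference. Neither is documented.

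What remains is that the named method discards observed data whenever a cell is empty, and nothing in the plan overrides it.

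**Conclusion.** The point holds in a limited form. The planned method excludes a child from each model with a missing cell, the protocol permits stopping at any time, and recruitment for Hypothesis 2 has no margin. On assumed independent missingness of 1% to 5% per staircase, the loss of Hypothesis 2 power runs from about 1 percentage point (two staircases, 1%) to about 25 (ten staircases, 5%). The upper end needs a single ten-threshold model, a separate isolated-letter staircase and no clustering, none of which the documents state. A child who stops early tends to miss several thresholds at once, which gives fewer incomplete children for the same rate. Selection towards children who find the tests easy is a reasonable worry, of unknown size.

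**What to change.** In Statistical consideration and Data management and analysis:

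1. Replace repeated-measures ANOVA as the main analysis with a linear mixed model fitted by REML to all observed thresholds. Use fixed effects for group, eye, test and their interactions, plus age and eye tested first.
2. Specify an unstructured or heterogeneous within-child covariance, or at least random child and eye-within-child effects with test-specific residual variances. Use Kenward-Roger or Satterthwaite degrees of freedom. A random child intercept alone is not enough: it imposes compound symmetry and gives up the sphericity protection that the plan now has. With ten thresholds a fully unstructured matrix has 10 × 11 / 2 = 55 parameters, which is heavy for 63 children, so name the simpler structure in advance as the fallback.
3. State which thresholds enter each model.
4. Keep the Huynh-Feldt-corrected complete-case ANOVA as a sensitivity analysis.
5. Report missing thresholds, with reasons, by test, eye and group.

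**Cost.** Wording only. SPSS, already named, fits mixed models, and no extra measurements are needed. The downside is a few more covariance parameters and reliance on data being missing at random. A threshold missing because the child could not do the test may break that assumption, so such cases should be reported separately.
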